### 5.2.5 Other safety parameters

Assessment of disease state:

PANSS will be used to evaluate the disease severity. Refer to [Section 5.2](#). In addition investigator may use CGI-S and his/her clinical judgment for assessing schizophrenia worsening/relapse.

**Schizophrenia worsening (i.e., deterioration of chronic residual symptoms):** Fluctuation in the severity of symptoms is common and should be managed and reported as per the clinical judgment of the investigator. Adjustment of background medication is allowed when necessary. In such cases, schizophrenia worsening must be reported as adverse event per the clinical judgment of the investigator.

**Schizophrenia Relapse (acute episode):** If **severity** of schizophrenia symptoms fulfills the criteria of relapse (acute episode), investigator must report relapse as adverse event. Definition of relapse for this program is: Increased level of care (such as hospitalization, home hospitalization, emergency room (ER) visit due to psychotic symptoms) due to worsening of psychotic symptoms / increased PANSS per investigators judgment.

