## **7. STATISTICAL METHODS AND DETERMINATION OF SAMPLE SIZE**

The primary efficacy objective is to assess the absolute difference in adjusted mean change from baseline to Week 26 in MCCB overall composite T-score (cognition) for once daily oral treatment with Iclepertin 10mg QD as compared with placebo in patients with CIAS. The key secondary efficacy objectives are to assess the absolute difference in adjusted mean change from baseline to Week 26 in SCoRS interviewer total score and adjusted total time T-score in VRFCAT between Iclepertin 10mg QD and placebo. Intercurrent events will be addressed using a strategy that differs depending upon the nature of the intercurrent event.

The treatment effect for the following treatment policy is of interest: patients remain on randomized treatment for the duration of the trial unless an exacerbation or acute episode or an event considered to be drug-related interrupts or discontinues treatment. Changes in background medication or non-pharmacological intervention are allowed.

Estimation will assume that the policy is followed by all randomized patients. All measurements obtained for patients while on this policy are therefore relevant for the estimation of the primary estimand, while measurements obtained after a deviation from this policy are not relevant for the estimation of the primary estimand.

The following intercurrent events are considered to form part of the treatment policy being assessed and hence subsequent measurements are included in the primary analysis of the endpoint:

- Change in background medication (e.g. antipsychotics, etc)
- Change in non-pharmacological therapy (e.g. cognitive therapy, any kind of psychotherapy, nicotine withdrawal therapy, diet, etc)
- Exacerbation or acute episode which results in interruption or early termination of treatment
- Investigator assessed drug-related adverse events which lead to early termination of study medication
- Protocol-defined drug withdrawal due to treatment, e.g. haemoglobin decrease, concomitant medications with CYP3A4 substrates
- Change in study partner in the assessment of functional capacity, e.g. SCoRS

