6.3 INTERCURRENT EVENTS

Definition and technical specification of protocol defined intercurrent events (ICEs) are listed in [Table 6.3: 1](#). In general, when handled under the hypothetical approach, data collected during the off-treatment period of an ICE will be considered irrelevant to the estimand and excluded from the analysis. While off-treatment data will be excluded, the patient will still be considered as on-treatment (hypothetically) from an analysis perspective by the statistical models, and during any imputations.

For an ICE of temporary treatment discontinuation or interruptions, the off-treatment period spans from the last treatment administration prior to the interruption + REP to the restart of

the study medication. For an ICE of early permanent treatment discontinuation, the off-treatment period starts from the last treatment administration + REP. [Figure 6.3: 1](#) illustrates the on-/off-treatment status after each type of ICEs. When there is more than one ICE of early permanent treatment discontinuation, any treatment policy ICE take precedence in data and analysis handling over any hypothetical ICE.

ICEs of change in concomitant therapies and other ICEs will always be considered as part of the treatment policy in the primary and all supplementary estimands. ICEs of this category will not affect the on-/off-treatment status which is only determined by changes in the study medication. These ICEs will be listed and summarized descriptively but will not be explicitly accounted for in the inferential analysis of efficacy.

Table 6.3: 1 Definition and technical specification of intercurrent events

Type of Intercurrent Event	Definition and Documentary Sources	Handling under the Primary Estimand
Temporary Treatment Discontinuations or Interruptions		
Exacerbation or acute episode of schizophrenia resulting in interruption of treatment	
Identified from data collected in the Temporary Trial Treatment Discontinuation and Adverse Event pages of the CRF:
 
 - Temporary discontinuation of trial treatment reported with reason being “Adverse Event”, and - AE category reported as “Schizophrenia Relapse” or MedDRA preferred term coded as “Schizophrenia” 	Treatment policy

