Temporary treatment discontinuation or interruption due to other reasons	Identified from data collected in the Temporary Discontinuation page of the CRF.	Hypothetical – only data collected from the end of REP after the interruption, to end of the interruption will be subject to exclusion from the analysis
Temporary treatment-switch due to dispensation error	Identified from the dispensation records. Temporary treatment-switch will be handled as temporary interruptions in the same way for both directions (iclepertin to placebo or placebo to iclepertin)	Hypothetical – only data collected from the end of REP after the treatment switch, to end of the treatment switch will be subject to exclusion from the analysis
Early Permanent Treatment Discontinuation		

Exacerbation or acute episode of schizophrenia resulting in early termination of treatment	Identified from data collected in the Adverse Event page of the CRF: 
 - “Drug Withdrawn” reported in the Action Taken with Study Treatment field, and - Category reported as “Schizophrenia Relapse” or MedDRA preferred term coded as “Schizophrenia” 	Treatment policy
Investigator assessed drug-related adverse events which lead to early termination of study medication	Identified from data collected in the Adverse Event page of the CRF: 
 - “Drug Withdrawn” reported in the Action Taken with Study Treatment field, and - “Yes” reported in the Relationship to Study Treatment field 	Treatment policy
Protocol-defined drug withdrawal due to treatment – haemoglobin decrease	Identified from data collected in the End of Treatment and Adverse Event pages of the CRF and laboratory data: 
 - Subject who did not complete the planned treatment period as reported in the End of Treatment page with reason being “Adverse Event”, and - AE indicating haemoglobin decrease with action taken being “Drug Withdrawn” 	Treatment policy
Protocol-defined drug withdrawal due to treatment – CYP3A4 inhibitors or CYP3A4 sensitive drugs with NTI	Identified from data collected in the End of Treatment page of the CRF: 
 - Subject who did not complete the planned treatment period as reported in the End of Treatment page with “Protocol Deviation” as the reason, and - Use of CYP3A4 inhibitors or CYP3A4 sensitive drugs with NTI specified as the detailed reason of discontinuation 	Treatment policy

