Early termination of study	Identified from data collected in the End of Treatment page of the CRF:	Hypothetical

[figure not shown]
medication due to other AEs	
 - Subject who did not complete the planned treatment period as reported in the End of Treatment page with reason being “Adverse Event” and not otherwise covered by any of the ICEs above. 	
Early termination of study medication due to perceived lack of efficacy	
Identified from data collected in the End of Treatment page of the CRF:
 
 - Subject who did not complete the planned treatment period as reported in the End of Treatment page with reason being “Perceived Lack of Efficacy”. 	Hypothetical
Early termination of study medication due to other reasons	
Identified from data collected in the End of Treatment page of the CRF:
 
 - Subject who did not complete the planned treatment period as reported in the End of Treatment page for reasons not covered by any of the ICEs above. 	Hypothetical

Change in Concomitant Therapies and Other ICEs

Change in background medication	
Identified from data collected in the Concomitant Medications page of the CRF:
 
 - Start of a new or stop of an on-going antipsychotic, benzodiazepines (or derivatives), anticholinergics, antiepileptics, or antidepressants during the on-treatment period, or - Change of dosage or dosing frequencies of an on-going antipsychotic, benzodiazepines (or derivatives), anticholinergics, antiepileptics, or antidepressants during the on-treatment period 
See Table 10.7: 1 for definitions of antipsychotics, benzodiazepines (or derivatives), anticholinergics, antiepileptics, and antidepressants.
	Treatment policy
Change in psychotherapy	Identified from data collected in the Psychotherapy page of the CRF:	Treatment policy

	
 - Change in frequency, setting or session of a psychotherapy during the on-treatment period 	
Change in other non-pharmacological therapy	
Identified from data collected in the Concomitant Non-Drug Therapies page of the CRF:
 
 - Start of a new non-drug therapy or stop of an on-going non-drug therapy during the on-treatment period 	Treatment policy

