	Generalised tonic-clonic seizure	Substance-induced psychotic disorder
	Hangover	Treatment noncompliance
	Intentional product misuse	Withdrawal syndrome
Euphoria-related adverse events	Dizziness	Feeling drunk
	Euphoric mood	Feeling of relaxation
	Feeling abnormal	Inappropriate affect
CNS depressant effects	Depressed level of consciousness	Sedation
	Fatigue	Sluggishness
	Hypersomnia	Somnolence
	Lethargy	Stupor
	Loss of consciousness	
Stimulation and anxiety-related adverse events	Agitation	Morbid thoughts
	Anxiety	Nervousness
	Anxiety disorder	Panic attack
	Anticipatory anxiety	Panic disorder
	Energy increased	Panic reaction
	Fear	Psychogenic tremor

	Fear of death	Psychomotor hyperactivity
	Feeling jittery	Restlessness
	Generalised anxiety disorder	Tension
	Hypervigilance	
Perceptual disturbances / psychotomimetic effects	Abnormal dreams	Hypoesthesia
	Acute psychosis	Ideas of reference
	Aggression	Illogical thinking
	Alice in wonderland syndrome	Illusion
	Altered state of consciousness	Incoherent
	Altered visual depth perception	Indifference
	Anger	Jamais vu
	Communication disorder	Loose associations
	Confusional state	Magical thinking
	Consciousness fluctuating	Nightmare
	Déjà vu	Paranoia
	Delirium	Paroxysmal perceptual alteration
	Delusion	Psychotic behaviour
	Delusion of grandeur	Psychotic disorder
	Delusion of reference	Psychotic symptom
	Delusion of replacement	Reactive psychosis
	Delusional perception	Rebound psychosis
	Derailment	Sensory disturbance
	Disinhibition	Sensory level abnormal
	Disorientation	Slow speech
	Dysarthria	Somatic delusion
	Flight of ideas	Somatic hallucination
	Formication	Staring
	Hallucination	Suspiciousness
	Hallucination, auditory	Tangentiality
	Hallucination, gustatory	Thinking abnormal
	Hallucination, olfactory	Thought blocking
	Hallucination, synaesthetic	Thought broadcasting
	Hallucination, tactile	Thought insertion
	Hallucination, visual	Thought withdrawal
	Hallucinations, mixed	Transient psychosis
	Hostility	
Dissociation	Daydreaming	Hypogeusia
	Depersonalisation/derealisation disorder	Metamorphopsia
	Derealisation	Ocular discomfort
	Diplopia	Oral dysaesthesia
	Dissociation	Oral hyperesthesia

	Dissociative disorder	Pain threshold decreased
	Dissociative identity disorder	Paraesthesia
	Dysaesthesia	Paraesthesia oral
	Dysaesthesia pharynx	Pharyngeal hypoesthesia
	Dysgeusia	Pharyngeal paraesthesia
	Dysmetropsia	Photophobia
	Feeling cold	Photopsia
	Feeling hot	Synaesthesia

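### SAP Table 6.3: 1 recognises an exacerbation only by the relapse category or one preferred term, so some stops for psychotic worsening fall outside treatment policy

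*SAP*

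**What the plan says.** Protocol Section 7 lists the intercurrent events that belong to the treatment policy. One of them is "Exacerbation or acute episode which results in interruption or early termination of treatment". The synopsis and Section 2.1.1 name exacerbation and an acute episode as separate items.

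Protocol Section 5.2.5 distinguishes two kinds of deterioration. Relapse is equated with an acute episode and requires an increased level of care. Worsening is a deterioration of residual symptoms, for which background medication may be adjusted: "In such cases, schizophrenia worsening must be reported as adverse event per the clinical judgment of the investigator".

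SAP Table 6.3: 1 turns the estimand into data rules. For a permanent stop, the adverse event must carry the drug-withdrawn action and meet this test: "Category reported as “Schizophrenia Relapse” or MedDRA preferred term coded as “Schizophrenia". The interruption row uses the same two-way test: "AE category reported as “Schizophrenia Relapse” or MedDRA preferred term coded as “Schizophrenia".

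Two further SAP 6.3 provisions keep data. One row, also under treatment policy, covers "Investigator assessed drug-related adverse events which lead to early termination of study medication". For multiple permanent-discontinuation events, "any treatment policy ICE take precedence in data and analysis handling over any hypothetical ICE". What remains goes to the row for other adverse events, defined as "not otherwise covered by any of the ICEs above" and handled as hypothetical. Interruptions for other reasons are also hypothetical.

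**The concern.** The data rule is narrower than the estimand it implements. For worsening that does not reach relapse, the only route into the exacerbation row is the single preferred term Schizophrenia. Two patients who stop for the same clinical reason could then be handled differently because one event was coded as Schizophrenia and the other as Psychotic disorder.

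Under the hypothetical strategy the later data are removed, and SAP 6.3 has the models and any imputation treat the patient as still on treatment. What is lost is the off-treatment outcome that the estimand means to include. If worsening were more frequent in one arm, the Week 26 contrast could move away from the stated estimand. SAP 7.5.1.1 applies the same strategy to SCoRS and VRFCAT.

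**Working it through.** **Tracing one case through Table 6.3: 1.** Take a permanent stop for psychotic worsening, with no relapse category, a preferred term other than Schizophrenia, and no drug relationship in the investigator's view.

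1. Exacerbation row: not met, since both branches of the test fail.
2. Drug-related row: not met.
3. Haemoglobin and CYP3A4 rows: not applicable.
4. Other adverse events: met, so hypothetical.

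Change any one of the three conditions (relapse ticked, preferred term Schizophrenia, or judged drug-related) and the case returns to treatment policy.

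**Are other terms foreseeable?** SAP Table 7.8.1: 1 lists "Acute psychosis", Psychotic disorder, Psychotic symptom, Psychotic behaviour, and several hallucination, delusion and paranoia terms as separate preferred terms. That table serves abuse-potential evaluation. It shows that the terms exist, not how often sites would use them for worsening. By contrast, the haemoglobin row of Table 6.3: 1 is defined by a concept rather than one term, and anaemia and drowsiness have term lists in SAP 7.8.1.

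**Which data are lost?** The excluded period starts at last dose plus the residual effect period of 12 days (SAP 6.1 and 6.3).
- The early end-of-treatment visit is preferably within 7 days of last dose (Protocol 6.2.5.1), so it is normally kept.
- The Week 26 window for MCCB, SCoRS and VRFCAT opens on Day 127 (SAP Table 6.7: 1). Since 127 − 12 = 115, retained data can reach that window only if the last dose is on about Day 115 or later.
- After an earlier stop, the retained early visit maps to Week 12. Any Visit 11 result, which Protocol 3.3.4.2 asks sites to collect, is not used.
- For an interruption, exclusion ends at restart. With planned post-baseline MCCB visits at Weeks 12 and 26, the Week 26 value is rarely affected.

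**Sensitivity analyses.** Protocol 7.2.2 applies the same intercurrent-event strategy. The first sensitivity analysis imputes from off-treatment data only after stops for exacerbation, acute episode or a drug-related event. A case sent to the wrong row would be imputed from on-treatment data instead.

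**Size.** The plan's own power figure comes first. With n = 220 per arm, standardised effect 0.35 and one-sided alpha 0.025:

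power = Φ(0.35 × √(220/2) − 1.96) = Φ(3.671 − 1.960) = Φ(1.711) = 95.6%, as in Protocol Table 7.5: 1.

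Inputs from Protocol 7.5: 586 randomised, 30% to 40% stopping early, and 25% to 50% of those with later outcomes. Assumption, not in the documents: 1% to 10% of early terminators are unticked, unrelated stops for worsening coded elsewhere.

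- Early terminators: 0.30 × 586 = 176 to 0.40 × 586 = 234.
- Affected: 0.01 × 176 = 1.8 to 0.10 × 234 = 23.4.
- With later outcomes: 1.8 × 0.25 = 0.4 to 23.4 × 0.50 = 11.7.
- Effective n per arm, if all are lost from the 220: 220 − 0.4/2 = 219.8 to 220 − 11.7/2 = 214.1.
- Power at 0.35: 95.6% to 95.2%.

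The upper end probably overstates the loss. The 25% to 50% refers to outcomes collected after treatment termination, which can include early end-of-treatment visits inside the 12 days.

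**The case against.** The strongest defence is that the rule may already match the estimand. Neither document defines exacerbation. A footnote to inclusion criterion 3 speaks of home hospitalisation for exacerbation, which ties the word to a raised level of care. On that reading, every exacerbation is a relapse and the relapse category captures it whatever its term. The branch for the preferred term Schizophrenia would then plausibly catch worsening reported under the name the protocol gives it. This has force. It does not close the point, because the synopsis and Section 2.1.1 list exacerbation beside an acute episode, and Section 5.2.5 equates only the acute episode with relapse. An undefined word should not decide whether primary-endpoint data are used.

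A reader might infer that Section 5.2.5 leaves the wording of a worsening event to the investigator, so that scattered coding is to be expected. It does not say so: judgement governs the reporting, and the event itself is named.

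A reader might also infer that interruptions add materially to the problem. They have no drug-related row, but exclusion ends at restart, so Week 26 is normally untouched.

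Protocol 7.2.2 also plans a supplementary analysis with all intercurrent events under treatment policy, which would keep every disputed observation. That gives a check on robustness, but it targets a different estimand and does not correct the primary classification.

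**Conclusion.** The point holds in a limited form. The SAP's rule is narrower than a reasonable reading of the protocol's estimand. It misses permanent stops that are unticked, coded to another psychosis term and not judged drug-related, and it costs such patients their data beyond last dose plus 12 days.

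The tempting stronger reading is that all stops for psychotic worsening coded outside Schizophrenia are censored and that the primary result is therefore biased. The documents do not support it. Relapse-ticked events, drug-related permanent stops and data inside the residual effect period are kept. That the estimand covers worsening short of relapse is an inference, though a sound one. No rate is given, no bias can be computed, and its direction would depend on whether worsening differs by arm.

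The number affected is unknown and probably small. Power is essentially unchanged at 95.2% to 95.6% under the assumed shares. What is at stake is fidelity to the primary and key secondary estimand. One limit remains: Figure 6.3: 1 and the CRF instructions are not available here, and a rule there for completing the relapse category could narrow the gap further.

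**What to change.** Before treatment information is released, amend SAP 6.3 in three ways.

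1. State that exacerbation includes worsening of schizophrenia that leads to interruption or withdrawal of trial medication.
2. In both exacerbation rows of Table 6.3: 1, add a pre-specified list of psychosis preferred terms that flags stops and interruptions linked to an adverse event. Candidates are Psychotic disorder, Acute psychosis, Psychotic symptom, Psychotic behaviour, and the hallucination, delusion and paranoia terms.
3. Classify a flagged event as an exacerbation when blinded medical review confirms that it reflects the underlying schizophrenia.

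The list should flag cases and not classify them automatically, because the same terms can describe drug effects. The cost is SAP wording, a term list and a short blinded review with some judgement on borderline terms. No new data are needed.

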6.4 SUBJECT SETS ANALYSED

The following patient analysis sets are defined:

- **Screened Set (SS):** includes all patients who signed informed consent and were screened for the trial with at least one screening procedure done at Visits 1 or 1a.

- Randomised Set (RS): includes all patients who signed informed consent and were randomised into the trial, regardless of whether a patient was treated with trial medication. Patients randomized in error and discontinued from the study before the start of trial medication will be excluded from the RS. Patients in RS will be analysed under the randomized trial medication. The RS will be used for efficacy analyses as well as demographics and baseline characteristics.
- Treated Set (TS): includes all patients who signed informed consent and were treated with at least one dose of the trial medication. Patients in TS will be analysed under the actual trial medication received at randomisation. The TS will be used for safety analyses.
- PK parameter analysis Set (PKS): includes all treated patients who have at least one evaluable PK plasma concentration measurement.
- Ocular sub-study Set (EYE): includes all treated patients who consented to participate in the ocular sub-study (including late/retrospective consent to the ocular sub-study) and had evaluable ophthalmologic measurements. The Ocular sub-study Set will be used for safety analyses, demographics, baseline characteristics and ophthalmologic endpoint analyses of the ocular sub-study.

6.6 HANDLING OF MISSING DATA AND OUTLIERS

Missing or incomplete AE dates will be imputed according to BI standards (1). Missing data and outliers of PK data will be handled according to (2).

If not specified otherwise, missing data will not be imputed and will remain missing. Potential outliers will be reported and analysed as observed.

Handling and derivation of total/domain/subscale scores for the assessment scales in case of missing individual item scores are specified below:

MCCB

Handling of missing data in MCCB tests will follow the MCCB Manual (available in the ISF). See [Section 10.1](#) for detailed descriptions and imputation rules.

SCoRS

For the 20-item SCoRS assessment, if six or more of the 20 items have missing response, which includes the response of “N/A”, for a subject at a visit, then the SCoRS total score for that subject at that visit is missing. If five or less of the 20 items have missing response, which includes the response of “N/A”, for a subject at a visit, then the item with missing response will be imputed first with the average of the non-missing item values for the subject at the visit, and then SCoRS total score for the subject at the visit will be derived as the sum of the non-missing item values and the imputed item values.

PANSS

PANSS total and subscale scores will be calculated as sums of their constituting item scores. If $\leq 20\%$ of the items are missing in the calculation of the total or subscale scores, the missing items will be temporarily imputed with the mean of the non-missing item scores. The total or subscale score will then be calculated as the sum of the non-missing and imputed item scores.

For calculation of PANSS total score and the subscale scores, the maximum numbers of missing items allowed are:

PANSS total score:	6 out of 30
Positive Symptom:	1 out of 7
Negative Symptom:	1 out of 7
General Psychopathology:	3 out of 16
Marder Positive Factor:	1 out of 8
Marder Disorganized Thought Factor:	1 out of 7
Marder Negative Factor:	1 out of 7
Marder Uncontrolled Hostility/Excitement Factor:	0 out of 4
Marder Anxiety/Depression Factor:	0 out of 4

If more than the maximum allowed number of items are missing, the score will not be calculated.

PRECIS

PRECIS total score and domain scores will be calculated as averages of their constituting non-missing items. [Table 6.6:1](#) lists the minimum number of non-missing items required for

calculation of PRECIS total score and domain scores. If fewer items than the minimum requirement are non-missing, the corresponding total score or domain score will not be calculated and will be treated as missing.

Table 6.6: 1 PRECIS minimum non-missing items required for total/domain score calculation

		Minimum required non-missing items
		PRECIS (28-item version)
Domain	Memory	3 out of 6
	Communication	3 out of 4
	Self-Control	3 out of 3
	Executive Function	4 out of 4
	Attention	3 out of 6
	Sharp Thinking	3 out of 3
PRECIS total score		19 out of 26

